3.2.3 Study periods

[Table 3–1](#) shows which study periods are applicable to DE and LTFU subjects:

This document cannot be used to support any marketing authorization application and any extensions or variations thereof.
PUBLIC COPY

Table 3-1: Study periods

Period		Screening Period	Up-Titration Period			Evaluation Period							Down-Titration Period	Safety Period		
Subjects	Visit	ScrV	TV1	TV2	TV2	EV	MEV	FEV	MEV	FEV	MEV	YEV	...	FV/EDV	DTV	SV
			V1	V2	V3	V4	V5	V6	V7	...						
Subjects	DE	x	x	x	x	x	x	x	x	x	x	x	x	x	(x)	(x)
	LTFU					x	x	x	x	x	x	x	x	x	(x)	(x)
	Early Discontinuations												x	x	x	x

(x) – only applicable if the subject does not switch to another BRV study or is taking marketed drug after FV

The study is divided into 5 periods: Screening Period, Up-Titration Period, Evaluation Period, Down-Titration Period, and the Safety Period.

There is a Screening Period for all DE subjects. For DE subjects, this comprises assessments performed prior to the first dose of BRV in N01266. So start date of Screening Period is date of written informed consent and end date is the day before first dose of BRV (TV1-1). Although, patients in LTFU studies will not attend a screening visit, the screening information comprises information collected at various assessments during the core study and consequently will have been collected at different times depending on the domain. Domain specific information is detailed in Section 3.3.

The Up-Titration Period is only applicable to DE subjects, and the start date is the date of the first dose of BRV. The following algorithm is used to determine the end date:

- If the subject enters the Evaluation Period, the date 1 day prior to the EV is the end date
- If the subject does not enter Evaluation Period, the Up-Titration Period ends on the date of the final dose of BRV

For the Evaluation Period, the start date is the date of the first dose of BRV on or after the EV date, and the following algorithm is used to determine the end date:

- If the subject continues the study until it ends, the Evaluation Period ends on the date of FV
- If the subject prematurely discontinues the study, the date of EDV is the end date

A discontinued subject or a subject who completes the study but does not continue BRV treatment will be considered entering the Down-Titration Period only if the subject has a record of at least 1 dose of BRV after the date of EDV. The start date of the Down-Titration Period is set as 1 day after the date of EDV, and the Down-Titration Period ends on the date of the final dose of BRV (DTV).

A discontinued subject without any dosing of BRV after the EDV will not have participated in the Down-Titration Period, and no artificial Down-Titration Period will be created for the purpose of analysis.

A discontinued subject is considered to have entered the Safety Period if the subject has at least 1 contact (scheduled visit, unscheduled visit (UV), or telephone contact) after the date of the final dose (DTV). The Safety Period starts 1 day after the date of the final dose of BRV irrespective of entering the Down-Titration Period, and end date is the date of last contact with the subject.

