2 PROTOCOL SUMMARY

This is a Phase 3, open-label, single-arm, multicenter, long-term study to evaluate the safety and efficacy of brivaracetam (BRV) in children with epilepsy. This study is designed for pediatric subjects ≥ 1 month to <17 years of age who have completed other pediatric BRV studies (herein referred to as “long-term follow-up” [LTFU] subjects) and for at least 100 subjects ≥ 4 years to <17 years of age with partial-onset seizure (POS) who had not previously enrolled in a pediatric BRV study (herein referred to as “directly enrolled (DE) subjects”), with a planned total enrollment of approximately 600 subjects.

The primary objective is to document the long-term safety and tolerability of BRV. The secondary objective is to assess the efficacy of BRV during long-term exposure. The other objectives are to explore direct cost parameters and to assess the effect of BRV 1) on behavior and cognition using the age-appropriate Achenbach Child Behavior Checklist (CBCL/1½-5 or CBCL/6-18) for LTFU subjects ≥ 18 months of age at Baseline of their initial BRV study (herein referred to as their “core study”) and for all DE subjects, 2) on cognition using the Behavior Rating Inventory of Executive Function® (BRIEF®)/BRIEF®-Preschool Version (BRIEF®-P), and 3) on quality of life using the Pediatric Quality of Life Inventory™ (PedsQL™) for LTFU subjects ≥ 2 years of age at the Baseline of the core study and for all DE subjects. The Bayley Scales of Infant and Toddler Development®, Third Edition (Bayley-III®) will be used to assess LTFU subjects enrolled in English-speaking countries and in countries where a validated

translation is available and <18 months of age at Baseline of the core study; the Bayley-III will not be used to assess DE subjects since all are to be ≥ 4 years of age.

The LTFU subjects will enter directly into the Evaluation Period at the Entry Visit (EV) and will continue BRV treatment at the individualized dose they were receiving at the completion of their core study. Directly enrolled subjects will enter N01266 at the Screening Visit (ScrV) and then participate in up to 3 weeks of an Up-Titration Period. If a DE subject demonstrates, in the opinion of the Investigator, acceptable tolerability and seizure control on the same daily dose of BRV (no lower than 1mg/kg/day) for 7 ± 2 days during the Up-Titration Period, the subject will attend the EV and enter the Evaluation Period on that dose.

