In case of early discontinuation, after the EDV, or for subjects who complete the study but do not continue BRV treatment, the Down-Titration Period starts with scheduled Down-Titration Visits (DTV). Dose will be down titrated by a maximum of half the dose every week for a maximum of 4 weeks until a dose of 1mg/kg/day is reached.

After 2 weeks free of study drug, the Safety Period, subjects will complete the Safety Visit (SV).

The study is defined to be completed if the study status on the study termination form is marked as completed. This indicates that all planned visits have taken place. Planned visits are dependent on whether a subject discontinues the study or not, and on whether a subject goes into another study or takes marketed drug after FV.

At each visit, the subject/parent(s)/legal representative(s) will receive a DRC, which has to be filled in daily by parent(s)/legal representative(s) or subject, if applicable, and returned at the next visit. No DRC will be dispensed at the SV or the FV.

The date and the number of epileptic seizures will be recorded on the DRC, as well as the type of seizure (according to individual description of seizures), occurrence of clusters, intake of concomitant AEDs, undesirable events with start and end dates, health care provider consultations not foreseen per protocol, and changes in concomitant medication, if applicable.

The written information will be discussed with the subject/parent(s)/legal representative(s) at each visit in order to ensure completeness and accuracy. As a result of the discussion, the Investigator will assess the seizures according to the International League Against Epilepsy (ILAE) codes and record the seizure types and frequency on the electronic case report form (eCRF); he/she will also confirm the presence of AEs (if applicable). Concomitant medication changes, health care provider consultations not foreseen per protocol, and AEs will be reported by the Investigator on the specific pages of the eCRF.

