3.2 General study level definitions

3.2.1 Analysis time points

3.2.1.1 First and final dose of study drug

Unless otherwise noted, all references to the first dose of study drug in this SAP refer to the first dose of study drug during N01266 (i.e., not the first dose of study drug from the core study in which subjects participated prior to N01266 for LTFU subjects). Unless otherwise noted, all references to the final dose of study drug in this SAP refer to the final dose of study drug taken across all study periods (ie, the final dose of study drug across the Up-Titration, Evaluation, and Down-Titration Periods).

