8.2.2 Incidences of TEAEs

Incidence summaries will be presented by SOC and PT. These tables will include the number and percentage of subjects and number of events by SOC and PT. For the number of subjects by PT, if a subject experiences multiple AE within the same PT, then that PT will only be counted once. As with the PT, for the number of subjects by SOC, if a subject experiences multiple AEs within the same SOC, then that SOC will be counted only once. Percentages will be calculated out of the number of subjects at risk in the SS unless otherwise stated.

Incidence tables are sorted alphabetically by SOC and decreasing by frequency in PT in the overall column. In case of ties, PTs are sorted alphabetically.

The following TEAE summaries will be presented:

- Incidence of TEAEs

- Incidence of TEAEs by 3-month time interval (one table presenting TEAEs starting within time intervals and one presenting those ongoing in the time interval)
- Incidence of drug-related TEAEs by 3-month time interval
- Incidence of TEAEs by 1-year time interval
- Incidence of TEAEs by total duration of exposure cohort (as per categories defined in Section 3.2.7)
- Incidence of TEAEs by study period (Up-Titration, Evaluation, Down-Titration, Safety)
- Incidence of TEAEs by maximum intensity
- Incidence of drug-related TEAEs
- Incidence of serious TEAEs
- Incidence of drug-related serious TEAEs
- Incidence of TEAEs for TEAEs occurring in at least 5% of subjects
- Incidence of TEAEs by 3-month time intervals for TEAEs occurring in at least 5% of subjects
- Incidence of TEAEs by 3-month time intervals for TEAEs occurring in at least 5% of subjects by geographical region
- Incidence of non-serious TEAEs occurring in at least 5% of subjects
- Incidence of non-serious TEAEs occurring in at least 5% of subjects by geographical region
- Incidence of drug-related TEAEs occurring in at least 5% of subjects
- Incidence of drug-related TEAEs occurring in at least 5% of subjects by geographical region
- Incidence of TEAEs leading to permanent discontinuation of BRV
- Incidence of drug-related TEAEs leading to permanent discontinuation of BRV

Tables presenting incidence of TEAEs occurring in at least 5% of subjects will include only TEAEs occurring on or above the reporting threshold of 5% in any age group or geographical region.

Additionally, following incidence tables will be presented by total duration of exposure categories:

- Incidence of serious TEAEs

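### For a directly enrolled child who never enters the Evaluation Period, Up-Titration as written takes in any taper, and fully overlaps Down-Titration if there was an early discontinuation visit

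*SAP*

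**What the plan says.** Only directly enrolled (DE) subjects have an Up-Titration Period. For those who go on, it ends the day before the Entry Visit (EV). For those who do not, SAP Section 3.2.3 says: "If the subject does not enter Evaluation Period, the Up-Titration Period ends on the date of the final dose of BRV".

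Section 3.2.1.1 fixes what final dose means unless noted otherwise: "the final dose of study drug across the Up-Titration, Evaluation, and Down-Titration Periods". Section 3.2.3 notes nothing otherwise.

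The same section lets a discontinued subject enter Down-Titration "only if the subject has a record of at least 1 dose of BRV after the date of EDV". It then fixes the first day: "The start date of the Down-Titration Period is set as 1 day after the date of EDV". For the last day it returns to the same final dose: "the Down-Titration Period ends on the date of the final dose of BRV (DTV". It does not exclude subjects who stopped before the EV.

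Section 3.2.3.1 gives an order of priority between periods (Up-Titration, Evaluation, Down-Titration, Safety), but for outcomes that fit more than one period because the onset date is partial. Section 4.2 expects that some subjects will discontinue during Up-Titration.

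**The concern.** Two definitions in one section claim the same days. For a DE child who stops before the EV and then takes further brivaracetam (BRV), Up-Titration and Down-Titration end on the same date. An adverse event during the taper, with a complete onset date, belongs to both periods under the definitions, and the priority order does not reach it. If that order were applied anyway, Up-Titration would win and an event during dose reduction would be shown as one during dose increase.

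Safety is the primary objective and treatment-emergent adverse events (TEAEs) are a primary variable. The outputs exposed are:

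- The by-period table in Section 8.2.2: "Incidence of TEAEs by study period (Up-Titration, Evaluation, Down-Titration, Safety".
- The separate presentation of Up-Titration TEAEs for DE subjects (Section 8.2.1).
- The table of possibly clinically significant (PCST) vital signs (Section 8.4.1). Vital signs are taken at the Down-Titration Visit. The main PCST summary leaves out DE Up-Titration assessments, and the table is repeated for the Up-Titration Period. Read literally, a taper value moves from the first table to the second.
- Up-Titration response and seizure freedom as derived in Section 3.10.3.1. Seizure freedom requires zero counts up to the period's end date, so a seizure in the taper would make a child who was seizure-free until the EDV not seizure-free for Up-Titration.

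**Working it through.** The plan states no figure to reproduce; this is a check of date rules.

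**Rules as written**, with the first BRV dose as day 1, EDV day E and final dose day F:

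- Up-Titration, Evaluation Period not entered: day 1 to F (Sections 3.2.3 and 3.2.1.1).
- Down-Titration, if F > E: day E+1 to F (Section 3.2.3).
- Overlap: F − E days, which is the whole Down-Titration Period.
- Taper share of Up-Titration days: (F − E)/F.

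**Contrast.** For a child who enters the Evaluation Period, Up-Titration ends at EV−1 and Down-Titration starts at EDV+1. The overlap is 0 days, so the fault is confined to non-entrants.

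**Inputs.**

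- Up-Titration length (Section 2): DE subjects "participate in up to 3 weeks of an Up-Titration Period", so 21 days at most.
- Taper (Section 2.3.1): at most half the dose each week, "for a maximum of 4 weeks until a dose of 1mg/kg/day is reached", so 28 days at most.
- Recommended doses (Table 3-5): about 1.0, 2.0 and 4.0 mg/kg/day in Weeks 1, 2 and 3.
- Assumptions: the EDV falls at the end of the week of stopping, and each reduced dose is taken for one week.

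With maximum halvings, Week 1 is already at the level where the stated taper ends (0 steps), Week 2 is one step away and Week 3 two.

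| Stop | E | Taper days | F | Taper share of Up-Titration |
|---|---|---|---|---|
| End of Week 1 | 7 | 0 | 7 | 0% |
| End of Week 2 | 14 | 7 | 21 | 7/21 = 33% |
| End of Week 3 | 21 | 14 | 35 | 14/35 = 40% |
| End of Week 3, longest taper | 21 | 28 | 49 | 28/49 = 57% |

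The last row is the upper limit for a full three-week Up-Titration and needs slower steps than the maximum. A four-week taper after an earlier stop gives a larger share arithmetically (E = 8: 28/36 = 78%), but it pairs the longest taper with the lowest starting doses, so nothing here rests on it.

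**How many children.** The SAP gives no rate of stopping during Up-Titration. If 5% to 10% of 100 DE children did so (an assumption), that is 5 to 10, fewer once those without a taper are removed. With a denominator of 100, each reassigned child moves a DE Up-Titration percentage by 1/100, about 1 point.

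**With the boundary moved** to the earlier of E and F, Up-Titration lasts 7, 14 or 21 days in the rows above and the overlap is 0 in every row.

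**The case against.** The strongest reply is that the overlap needs an EDV, and the SAP does not settle whether a child who stops during Up-Titration has one. Sections 2 and 2.3.1 describe the EDV as part of the Evaluation Period, although the passage on early discontinuation in Section 2.3.1 is worded generally. Without an EDV, Down-Titration has no start date and nothing overlaps; Up-Titration is then all BRV exposure of a non-entrant, which could be a deliberate convention. This stands as a limit on certainty. It does not remove the point, because the taper is then labelled wholly as Up-Titration and the SAP does not say that this is intended.

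Three stronger readings are tempting, and the document does not support them:

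- A reader might infer that taper events will be counted twice. No passage instructs that. What is missing is a rule for fully dated events.
- A reader might infer that all Up-Titration safety tables are mixed. Laboratory summaries, and observed values and changes in vital signs, are repeated for Up-Titration visits rather than for the period (Sections 8.3 and 8.4.1). Laboratory PCST tables cover only the Evaluation and Safety Periods, and Section 8.4.2 schedules no ECG at the Down-Titration Visit. Only an unscheduled ECG could matter.
- A reader might infer distorted Up-Titration responder and seizure-freedom tables. Section 9 lists Up-Titration and Down-Titration efficacy data only, unless otherwise mentioned, and Section 9.2 tabulates response and seizure freedom for the Evaluation Period. The derived and listed values are affected, and so possibly is the separate Up-Titration seizure-count summary mentioned in Section 3.10.3.1.

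It is also fair to say that 57% is an extreme, and that a child who stops in Week 1 on the recommended schedule would have little or no taper.

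**Conclusion.** The period definitions conflict for a DE child who does not enter the Evaluation Period, has an EDV and takes BRV after it: the whole Down-Titration Period lies inside Up-Titration, and no stated rule assigns a fully dated event. If there was no EDV, the taper counts wholly as Up-Titration.

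The consequence is local. It touches TEAEs by study period, the Up-Titration TEAE presentation, the Up-Titration vital-sign PCST repeat, and derived or listed Up-Titration seizure variables. Overall TEAE incidence does not change, and quantitative laboratory summaries and scheduled ECGs are essentially unaffected. All analyses are descriptive, so no test or decision rule depends on it.

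For an affected child, 33% to 40% of Up-Titration days would be taper under the schedule assumptions above. The number of such children is unknown and probably small. The conclusion rests on the literal text of Sections 3.2.1.1 and 3.2.3; the protocol was not available to show whether an EDV is required in this case. It is worth correcting because the change is so cheap, not because the effect is large.

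**What to change.** In Section 3.2.3, reword the second bullet on the end of Up-Titration: for a DE subject who does not enter the Evaluation Period, the period ends on the date of the EDV, or on the date of the final BRV dose if that is earlier. Down-Titration, from the day after the EDV, then no longer overlaps it.

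That wording does not cover a child with no EDV. For that case the sponsor should reconcile the Up-Titration and Down-Titration definitions by stating to which single period doses after the decision to discontinue belong. If the taper is meant to count as Up-Titration, the Down-Titration definition needs a matching exclusion.

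The change concerns analysis-period boundaries only and touches no dosing or taper rule. It costs about one line of SAP text and one of code, plus a sentence for the case without an EDV. No new data are needed.

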3.2.3.1 Assignment of safety variables to study periods

In general, safety variables (e.g. AEs) will be allocated to the treatment group based on the dose most recently received. Safety outcomes which can be classified into more than 1 study period as per Section 3.2.3, based on partial dates of onset, will be classified into a study period based on the following prioritization: Up-Titration, Evaluation, Down-Titration, Safety, (for example, an AE that can be classified in both the Evaluation and Safety Period based on a partial date of onset due to a missing day entry, will be classified into the Evaluation Period).

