3.2.7 Exposure duration and exposure duration cohorts

The overall duration of exposure for each subject will be calculated as the date of the final dose of BRV minus the date of the first dose of BRV plus 1 day.

Each subject will be classified into 1 or more of the following exposure duration cohorts based on the duration of BRV exposure as calculated above:

Table 3–3: Exposure duration cohort definitions

Cohort	Definition
All subjects	≥ 1 day
> 3 months	> 90 days
> 6 months	> 180 days
> 9 months	> 270 days
> 12 months	> 360 days

This categorization will continue in 3-month increments past 12 months up to a time point that will be determined based on a review of cumulative exposure on the database performed prior to database lock (DBL).

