4.2 Handling of dropouts or missing data

The method for handling missing and partial data for medications and AEs is described in Section 3.10.4.1 and Section 3.2.3.1 respectively. Missing AE intensity or relationship will be imputed according to worst case scenario with severe intensity and assumed to be related. For other safety variables, no imputation methods are planned.

Regarding efficacy variables, endpoints using seizure frequency and seizure free days based on DRC data will be calculated over non-missing diary days during each study period or time interval as described in Section 3.10.3.1; days for which seizure diary data were not obtained will not be considered in the calculation of seizure frequency or seizure days. This is applicable to the analysis taking all seizure categories into account as well as to the analysis taking only POS seizures into account. Generally, compliance with the daily seizure diary is expected to be high in a refractory population and, therefore, the impact of missing diary data is expected to be minimal. Because the evaluation of efficacy is not the primary objective of this study, and because this is an uncontrolled study in a variable setting, which allows individualized optimization of dosing of BRV and concomitant AEDs, no summaries assessing the impact of missing seizure diary days are planned.

For subjects who prematurely discontinue during the Up-Titration, Evaluation or Down-Titration Period, the calculation of seizure frequency, seizure free days and seizure freedom will be based on available seizure diary days while the subject was receiving BRV. This effectively imputes the unobserved seizure frequency after discontinuation with the seizure frequency observed prior to discontinuation. The presence of such dropouts may influence the evaluation of the long-term outcomes for subjects who either do not discontinue or do not discontinue early in the study. Therefore, as described below, selected summaries will be produced by exposure duration cohorts to allow an assessment of long-term outcomes without the potentially confounding influence of earlier discontinuations.

Endpoints using seizure data from EEG will only include available data. No imputation method will be conducted.

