8.1 Extent of exposure

The Evaluation Period BRV exposure duration (in months) will be calculated as the date of the final dose of BRV during the Evaluation Period minus the date of the first dose of BRV in the Evaluation Period plus 1 day divided by 30. The overall study BRV exposure duration (in

months) including Up-Titration Period (only DE subjects), Evaluation Period and Down-Titration Period (only discontinued subjects) will be calculated as the date of the final dose of BRV in this study minus the date of the first dose of BRV in this study plus 1 day divided by 30.

Subject years of exposure are calculated as overall study BRV exposure duration (in months) multiplied by 30 divided by 360.

Both, the evaluation Period BRV exposure duration and the overall study BRV exposure duration will be summarized with quantitative descriptive statistics. The number and percentage of subjects with the following categories of Evaluation Period BRV exposure durations will also be presented: \leq 6 months, $>$ 6 to \leq 12 months, $>$ 12 to \leq 18 months, $>$ 18 to \leq 24 months, $>$ 24 to \leq 30 months, $>$ 30 to \leq 36 months, and $>$ 36 months.

The number and percentage of subjects exposed overall and by 6 month exposure durations (\leq 6 months of exposure, $>$ 6 months of exposure, $>$ 12 months of exposure, $>$ 18 months of exposure ...) will be presented overall and by modal dose category (see Section 3.2.8).

Additionally, the table will show mean subject years of exposure overall and by modal dose categories.

All BRV exposure data will be listed.

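### When brivaracetam stops before the Early Discontinuation Visit, the days between fall in both the Evaluation and Safety Periods, and the diary derivations run past the last dose although Section 4.2 stops them there

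*SAP*

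**What the plan says.** SAP Section 3.2.3 fixes the end of the Evaluation Period for early leavers by a visit: "If the subject prematurely discontinues the study, the date of EDV is the end date". It fixes the start of the Safety Period by a dose: "The Safety Period starts 1 day after the date of the final dose of BRV irrespective of entering the Down-Titration Period". Entry into the Safety Period needs only one contact after the final dose, and a scheduled visit counts as one. The section foresees subjects who do not taper: "A discontinued subject without any dosing of BRV after the EDV will not have participated in the Down-Titration Period".

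Section 3.2.3.1 gives an order of priority, but only for outcomes that could fall in several periods "based on partial dates of onset, will be classified into a study period based on the following prioritization: Up-Titration, Evaluation, Down-Titration, Safety".

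For seizure diaries, Section 4.2 says that in premature discontinuers seizure frequency, seizure-free days and seizure freedom "will be based on available seizure diary days while the subject was receiving BRV". Section 3.10.3.1, to which Section 9 refers for all efficacy derivations, evaluates diary counts from the Entry Visit to the EDV or Final Visit and mentions no cut at the last dose.

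Exposure is defined by doses. Overall it is "calculated as the date of the final dose of BRV minus the date of the first dose of BRV plus 1 day". Within the Evaluation Period it starts from "the date of the final dose of BRV during the Evaluation Period minus the date of the first dose of BRV".

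**The concern.** One boundary is tied to a visit and the other to a dose. If the last dose comes first, the two periods overlap, and nothing says where a fully dated event in the overlap belongs. It may be counted in both columns, or in one column at the programmer's choice.

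The outputs at stake are:

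- treatment-emergent adverse events (TEAEs) by study period (Section 8.2.2);
- the laboratory PCST (possibly clinically significant treatment-emergent) summaries, tabulated for the Evaluation and Safety Periods separately (Section 8.3);
- the 3-month adverse event intervals (Section 3.2.4).

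For efficacy, two programmers could follow two different sections and obtain different responder and seizure-freedom results for the same early leaver.

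**Working it through.** The SAP gives no figure for the gap between last dose and EDV, so all dates below are assumptions. Notation: Day 1 is the Entry Visit and first dose in a long-term follow-up subject, L is the day of the last dose, and E is the day of the EDV.

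**1. Overlap.** The Evaluation Period is Days 1 to E. The Safety Period is Day L+1 to last contact. An EDV held after the last dose is itself a contact, so the overlap is max(0, E − L).

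- L=80, E=80: 0 days
- L=79, E=80: 1 day
- L=80, E=87: 7 days
- L=80, E=100: 20 days
- L=170, E=185: 15 days
- L=100, E=80 (dosing continues after the EDV): 0 days

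The overlap arises only when dosing stops before the EDV. If the EDV is also the last contact, the whole Safety Period lies inside the Evaluation Period.

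**2. Tie-break.** The priority order in 3.2.3.1 is conditional on a partial onset date. An event with a complete date in Days L+1 to E meets both period definitions and does not trigger the rule.

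**3. Laboratory PCST.** Section 8.3 calls any abnormality seen in the Evaluation Period treatment emergent, so a value from Days L+1 to E qualifies. It also meets the Safety Period definition. The vital-sign PCST summary in 8.4.1 is cut at the final dose, so the two safety summaries use different rules.

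**4. Adverse event intervals, L=80 and E=100.** Section 3.2.4 includes a subject in an interval if the Evaluation Period ends on or after its first day. Since 100 ≥ 91, the subject is in the Months 4 to 6 denominator. Section 3.2.1.2 restarts the Entry Visit relative day after the last Evaluation dose, so an event on Day 95 is labelled +15 (95 − 80). That label fits no interval in Table 3-2, so the subject is in the denominator without a rule to place the event in the numerator. Exposure is 80 days (80/30 = 2.67 months), so the same subject is not in the >3 months (>90 days) exposure cohort.

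**5. Diary frequency and response.** Assume a Baseline of 1 seizure/day, 20 days on BRV at 0.45/day, then 1/day off BRV until an EDV on Day 30. Section 3.10.3.1 excludes the stop date, so Days 21 to 29 give 9 off-drug days.

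- On BRV only (4.2): 1 − 0.45 = 55% reduction, a responder.
- Full window to the EDV (3.10.3.1 without 4.2): (20×0.45 + 9×1)/29 = 18/29 = 0.621/day, a 37.9% reduction, not a responder. Off-drug share: 9/29 = 31%.

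**6. Seizure freedom.** Section 3.10.3.1 requires a diary on at least 90% of days up to the day before the period end, and zero counts through the end date. For the same dates and no seizures on BRV:

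- If off-drug days are used, one seizure on Days 21 to 30 sets the endpoint to 0.
- If off-drug days are dropped as 4.2 says but the denominator still runs to the EDV, diary completion is at most 20/29 = 69%. That is below 90%, so the endpoint is again 0. For L=80 and E=100 it is at most 80/99 = 80.8%, with the same result.

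**7. What does not move.** Overall and Evaluation Period exposure (3.2.7, 8.1), modal dose (3.2.8), Last Value (3.2.6) and the overall vital-sign PCST summary (8.4.1) all stop at the last dose. TEAE status in 3.10.1 has no end-of-treatment cut-off, so overall TEAE incidence is the same whichever period receives the event.

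**The case against.** The planned sequence is the EDV first and then down-titration, so the last dose normally follows the EDV and no overlap arises. The SAP gives no frequency or length for earlier stops. After long exposure a gap matters little: a 10-day gap after 1,080 days on drug leaves 9 off-drug diary days in the window, 9/1,089 = 0.8%. Section 4.2 is the specific rule for early leavers and can be read as overriding the general window. For average daily frequency and response both rules can be met by using only on-BRV days within the window, and the child in step 5 then keeps the 55% reduction. The combined Evaluation and Safety laboratory summary is unaffected, and efficacy is exploratory and untested.

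Most of this stands, and it limits the point. Two things remain. The SAP itself foresees subjects with no dose after the EDV, yet gives no rule for a fully dated event between last dose and EDV. For seizure freedom, the 90% and zero-count criteria are tied to the period end date, so restricting the diary to on-BRV days does not reconcile the sections.

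A reader might infer that off-drug days generally count as treated time, or that the primary TEAE results are distorted. The documents do not support either reading: exposure is measured from dose to dose, and overall TEAE incidence does not depend on period assignment.

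**Conclusion.** The definitions overlap by EDV minus last dose for every premature discontinuer who stops BRV before the EDV. The effect is confined to TEAEs by study period, the Evaluation/Safety laboratory PCST split and its treatment-emergent label, and the 3-month adverse event intervals. The conflict between 3.10.3.1 and 4.2 is a separate defect. It is firm for seizure freedom, and for frequency, response and seizure-free days it is a missing cross-reference.

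The fall from 55% to 37.9% rests on assumed dates and seizure rates, and applies only if 4.2 is not followed. It shows the direction and is not an estimate of the study's results. How many subjects are affected cannot be determined from the SAP. The correction is worth making before database lock because those affected are early stoppers and the SAP leaves their handling open.

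**What to change.** 1. In 3.2.3 and 3.2.3.1, set one non-overlapping boundary for fully dated safety events and laboratory values when the last dose precedes the EDV. One option is to assign those dated after the final dose to the Safety Period only. Use the same boundary for the numerators and denominators of the adverse event intervals in 3.2.4, and align the relative-day rule in 3.2.1.2 with it.
2. In 3.10.3.1, state that for premature discontinuers the diary window ends at the earlier of the final BRV dose and the EDV. Apply this to average daily frequency, response, seizure-free days and seizure freedom, including its 90% and zero-count criteria. This carries out what 4.2 already says.
3. Leave the mapping of EDV assessments to scheduled visits (3.2.9) and the questionnaire summaries unchanged. Moving all EDV assessments made after the last dose into the Safety Period would contradict that mapping and drop questionnaire scores that are summarized only for Evaluation Period visits.

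No new data are needed. The cost is SAP wording and minor reprogramming, and a few early stoppers change period or interval counts. With L=80 and E=100, the subject leaves the Months 4 to 6 adverse event denominator. If the diary-interval inclusion test in 3.2.4 uses the same cut, the subject also leaves the Months 1 to 3 diary interval, so 3.2.4 should state which end date that test uses.
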